#### 4.2.2.1. Reasons for Withdrawal/Early Discontinuation

A subject may decide to withdraw from the study at any time, for any reason, without prejudice to subsequent care or treatment by the Investigator. When this occurs, the subject should complete all the procedures for the Week 52 (EOT) Visit. Subjects who discontinue the treatment due to AEs should remain under observation until the resolution or stabilization of the AEs. A subject may be discontinued from the study drug treatment before completion for any of the following reasons:

- 1. Subject death
- 2. Subject experiences an AE(s)/SAE(s) that warrants discontinuation, as judged by the Investigator and/or Insmed Medical Director
- 3. A major protocol deviation, which, in the opinion/discretion of the Investigator and/or Insmed, compromises the data integrity of the study
- 4. Subject is noncompliant with the study drug treatment (defined as <80% compliance after at least 2 reeducation efforts)
- 5. Withdrawal by subject
- 6. Termination of the study by the Sponsor
- 7. Investigator discretion
- 8. Subject lost to follow-up
- 9. Subject pregnancy
- 10. Periodontal criteria met (see Section 9.10.3.2)
- 11. Skin criteria met (see Section 9.10.3.1)
- 12. Diagnosis of a malignancy during study, excluding carcinoma in situ of the cervix, or squamous or basal cell carcinoma of the skin
- 13. Serious infection, defined as any infection other than associated with a pulmonary exacerbation that:
  - a. Requires parenteral treatment with an antibiotic requiring admission to the hospital, or parenteral treatment with an antifungal, antiviral, antiparasitic, or antiprotozoal agent
  - b. Is opportunistic, such as TB or other infections whose nature or course may suggest an immunocompromised status
- 14. Subjects who develop neutropenia defined as ANC <1000/mm^3
- 15. Subjects who have the following:
  - a. ALT and/or AST values >3 × ULN and total bilirubin >2 × ULN, excluding confirmed Gilbert's Syndrome
  - b. Confirmed AST and/or ALT >5 × ULN (for more than 2 weeks).

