# 10.1. Sample Size and Power Considerations

The study is designed to demonstrate superiority of brensocatib treatment at 10 mg and/or 25 mg over matching placebo as measured by the primary efficacy endpoint of the rate of PEs over the 52-week treatment period. Assuming the annualized PE rate in the placebo arm is 1.2 events with a negative binomial distribution with dispersion of 1, 1620 adult subjects will yield 90% power if the ratio of exacerbation rate is 0.70 (brensocatib over placebo) between any of the brensocatib treatment arms and placebo after 52 weeks of treatment. This estimate is based on study-wise two-sided Type I error of 0.01 or 0.005 for each primary comparison between brensocatib and placebo.

Randomization will be stratified based on a geographic region (North America, Europe, Japan, and the Rest of the World), Screening sputum sample positive or negative for *Pseudomonas aeruginosa*, and the number of prior PEs  $(2, \text{ or } \ge 3)$  in the previous 12 months.

It is well known that among subjects with NCFBE, there is significant heterogeneity across regions in terms of distribution of phenotypes, baseline lung function, symptom scores, presence of comorbidities, and treatment patterns (Jauhiainen et al., 2020; Rabe et al., 2019). The ASPEN study was launched with a global outreach to more than 30 countries so that meaningful conclusions could be drawn on the effect of brensocatib in a representative population. Furthermore, the study was designed to ensure an adequate representation of all types of standards of care and of individual phenotypes worldwide.

In order to have a representative population of NCFBE across all regions, enrollment targets have been established for adult subjects. Up to 13% of subjects will come from Eastern Europe. North America, Western Europe, Asia Pacific, and Latin America will contribute between 20%

and 30% each. No single country (except the US) will contribute more than 15% of the overall randomized population.

In order to have a representative population in the study, similar to what is described in the literature, randomization will be enforced to have approximately 30% of adult subjects with 3 or more prior PEs, to have no more than 20% of subjects older than 75 years of age, to have approximately no more than 20% of subjects with eosinophil count in peripheral blood ≥300/mm³ at Screening, and to have no more than 20% of subjects with COPD as a comorbidity.

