## 3.2. Sample Size Determination

The study is designed to demonstrate superiority of brensocatib treatment at 10 mg and/or 25 mg over matching placebo as measured by the primary efficacy endpoint of the rate of PEs for adult participants over the 52-week treatment period ( $\geq$ 18 years and  $\leq$ 85 years of age [inclusive] at Screening). Assuming the annualized PE rate in the placebo arm is 1.2 events with a negative binomial distribution with dispersion of 1, a total of 1,620 adult participants randomized in a 1:1:1 ratio to brensocatib 10 mg, brensocatib 25 mg and matching placebo, respectively, will yield 90% overall power to demonstrate that at least 1 dose of brensocatib is superior to placebo under the Truncated Hochberg procedure (overall alpha = 0.01; two-sided test; truncation fraction = 0.9). The ratio of exacerbation rate is assumed to be 0.70 (brensocatib over placebo) between any of the brensocatib treatment arms and placebo after 52 weeks of treatment.

The PK/PD substudy is targeted to enroll approximately 300 participants; the sample size is based on clinical considerations and participant numbers for the PK study.

CONFIDENTIAL Page 19 of 139

<sup>bAdolescents=male or female participants, ≥12 years to <18 years of age at screening

The CT substudy is targeted to enroll approximately 225 adult participants; the sample size is based on clinical considerations and participant numbers for the CT study.

In addition, approximately 40 adolescent participants will be enrolled in a 2:2:1 randomization scheme (16:16:8) to minimize exposure to placebo treatment. The sample size is based on the Sponsor's consultation with several pediatric investigators in this field and from a survey across a number of global sites with pediatric experience conducted by the study contract research organization (CRO). The sponsor believes this proposed sample size will provide an adequate description of the safety profile of brensocatib in this age group and assessment of brensocatib exposure and offer the possibility to observe directional trends in terms of efficacy.

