#### 6.7.2. Responder Status for Exacerbation-Free over the 52-Week Treatment Period

For the On-Study Estimand, a participant will be defined as "Responder" / "Non-responder" based on exacerbation events that are confirmed through adjudication over the 52-week treatment period.

In order, to be a "Responder" participants must:

- complete 52-Weeks on study, AND
- have no exacerbation event that meets the protocol definition of PE diagnosis confirmed by an independent adjudication committee during the 52-Weeks.

If a participant has at least one PE confirmed through adjudication during the 52-Week study period, the participant will be classified as "*Non-responder*".

CONFIDENTIAL Page 41 of 139

For participants who discontinue the study prior to Week 52 without having experienced a PE confirmed through adjudication, their responder status will be imputed based on the observed data model (see Section 8.3.2.1).

For the Composite Estimand, the above criteria must be met, at a minimum, in order to be classified as "*Responder*". However, participants meeting one of the below criteria will be considered as "*Non-responder*", given no PE was observed prior to:

- Early discontinuation from randomized IP for the below reasons:
  - o Death due to NCFBE (to be investigated through the AE page)
  - Lack of efficacy
  - Tolerability; defined as discontinuation from randomized IP due to an AE which is deemed to be related to the randomized IP by the investigator; cases will be identified through the AE eCRF by looking for action="DRUG WITHDRAWN", relationship="RELATED"
- Addition of chronic antibiotics over the 52-Week Treatment Period

Early discontinuation from randomized IP for other reasons will follow the Treatment Policy strategy.

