### 8.2.2. Sensitivity Analyses – Tipping Point

If there are study participants who discontinue randomized IP early and decline to remain in the study, ascertainment of data will be incomplete, and a true Treatment Policy/ITT analysis cannot be achieved. A "missing at random" (MAR) assumption for the missing data is made implicitly for the On-Study Estimand.

The main analysis using the negative binomial model is unbiased under the MAR assumption for the missing data. However, in some instances, the fact that data are missing may be directly related to the unobserved values, i.e., missing not at random (MNAR). Therefore, robustness of the main analysis to departures from the MAR assumption will be assessed using tipping-point analyses. Due to the inherent difficulties in identifying the missing data mechanism in practice, all missing data will be assumed MNAR, and the tipping point penalties will be applied accordingly.

As the first step, multiple imputations (MI) of missing PE data under the observed data model (MAR assumption) will be implemented using negative binomial model, which models the distribution of a response Y, e.g., the number of PE events, as the joint distribution of the observed responses  $Y_{obs}$  and a distribution of the missing responses  $Y_{mis}$  after discontinuation from the study. Missing post withdrawal PEs will be imputed with the predicted PE values from the model, per treatment and strata, for the time remaining after study discontinuation prior to Week 52. Refer to Figure 2 as a visualization of the different periods of a participant's participation who discontinued early from study.

Figure 2: Sensitivity Analysis: Period of Discontinued Participants

CONFIDENTIAL Page 53 of 139

For a given participant, the conditional distribution  $Y_{mis}|Y_{obs}$  is a function of the observed events  $y_1$ , the estimated dispersion, the estimated PE rate in period 1 (which is the same as obtained in the primary analysis) and the model covariates. The imputed count of PEs will be combined with the observed PE count. The process of imputing missing PE data will be repeated multiple times to create 100 separate datasets.

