#### 8.3.2. Responder Status for Exacerbation-Free over the 52-Week Treatment Period

#### 8.3.2.1. Main Analyses

The Estimand of the responder status for exacerbation-free over the 52-week treatment period is the On-Study Estimand in which all observed data will be included in the analysis (see Section 2). The ITT Analysis Set (see Section 5.2) will be used for this Estimand. The derivation of the endpoint is detailed in Section 6.7.2.

The number and percentage of Responders/Non-responders over the 52-Week Treatment Period will be presented by treatment group.

Responder status at Week 52 will be compared between treatment groups brensocatib vs. placebo using a logistic regression model including treatment group, sputum sample being classified as positive or negative for *Pseudomonas aeruginosa* at Screening Visit, the number of prior PEs [<3 or ≥3] in the previous 12 months, stratification region (North America, Europe, Japan, and the Rest of the World), and age group (adult, adolescent) as fixed effects. If the age group covariate creates estimability issues, it may be removed. An estimate of the odds ratio for the treatment comparison (brensocatib 10mg vs. placebo; brensocatib 25mg vs. placebo) and the 95% Wald confidence interval will be summarized; the corresponding p-value from the Wald chi-square test will be compared to the appropriate alpha level per the multiple test procedure.

For participants who discontinue the study prior to Week 52 without having experienced a PE confirmed through adjudication, their responder status will be missing. To address this issue, first event times for these participants will be imputed based on the observed data model for the time period after discontinuation from the trial. If the imputed event time occurs prior to Week 52, the participant will be considered a non-responder. Otherwise, the participant will be considered a responder. The process of imputing missing PE data will be repeated multiple times to create 100 separate datasets. With each increment, the 100 complete data sets will each be analyzed using the logistic regression model described above. The analysis results will then be combined using Rubin's rules (Rubin 1987).

Technical details for the implementation in SAS can be found in Appendix I.

CONFIDENTIAL Page 59 of 139

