### **8.3.4.2.** Sensitivity Analyses

The analytical approach of the sensitivity analysis described in Section 8.2.2 will be applied for severe PEs with the difference, that death from any cause will be counted as a severe PE.

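### Deaths before Week 52 without an adjudicated PE are imputed like living dropouts, so a death can count as exacerbation-free success, and two tipping-point analyses impute PEs after death

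*SAP*

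**What the plan says.** **Responder rule.** SAP 6.7.2 sorts participants under the On-Study estimand into three groups.
- Responders meet two conditions: the first reads "complete 52-Weeks on study, AND" and the second is no adjudicated PE.
- Non-responders have at least one adjudicated PE.
- Those who leave early without a PE are imputed. SAP 8.3.2.1 puts it this way: "For participants who discontinue the study prior to Week 52 without having experienced a PE confirmed through adjudication, their responder status will be missing". Their first-PE time is drawn from the observed-data model. A time before Week 52 makes them non-responders and anything later makes them responders (Day 365 is the cut in Appendix I). One hundred data sets are analysed and combined.

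**Death.** It is not one of the two intercurrent events in SAP 6.2.1. Protocol 4.2.2.1 lists "Subject death" first among its reasons. That list is worded as reasons for stopping study drug, but the section then groups death with consent withdrawal and loss to follow-up as exceptions to continued visits. Only the supplementary Composite estimand names death as non-response, and only death due to NCFBE.

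**Tipping-point analyses.** SAP 8.2.2 imputes PEs "for the time remaining after study discontinuation prior to Week 52". Appendix I (Table 19 and the modelling assumptions) gives early leavers a total of one year, so T2 = 1 − T1, and draws the unobserved count Y2 with k* = 1/c + Y1. SAP 8.3.4.2 applies the same approach to severe PEs with one change: "death from any cause will be counted as a severe PE". Under SAP 6.2 these analyses are run only if the main result is significant.

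**The concern.** A participant who dies PE-free before Week 52 has not completed the study and has had no PE, so only the imputed group is left. The reasons given for imputing do not fit a death. SAP 8.2.2 argues from people who stop treatment and choose not to stay on; Appendix I argues from what would have happened had the participant stayed. No text states a hypothetical strategy for death.

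The endpoint is Family 3 of the testing procedure (H5 and H6), so a death can enter as success in a confirmatory comparison. The advantage goes to whichever arm has more PE-free deaths. A rule for deaths chosen after unblinding would look data-driven.

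In 8.3.4.2 the participant's death is already an event. The rule as written then adds events for time in which no event is possible, and adds more of them because the death sits in Y1.

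**Working it through.** **Inputs.** Protocol 10.1: "Assuming the annualized PE rate in the placebo arm is 1.2 events with a negative binomial distribution with dispersion of 1", with "study-wise two-sided Type I error of 0.01 or 0.005 for each primary comparison between brensocatib and placebo". SAP 3.2: rate ratio 0.70, so the brensocatib rate is 1.2 × 0.70 = 0.84 per year; 540 per arm; 52 weeks. Protocol 1.2.2.3 (Phase 2): 48.3%, 31.7% and 33.3% on placebo, 10 mg and 25 mg had a PE in 24 weeks, and 1 of 256 died. The documents give no expected death, dropout or severe-PE rate for this trial, so those used below are assumptions.

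**1. The plan's own figure.** Var(log RR) = [(1/1.2 + 1) + (1/0.84 + 1)]/540 = 4.024/540 = 0.00745, so SE = 0.0863. Then 0.3567/0.0863 = 4.13. Against 2.81 (two-sided 0.005), power is Φ(1.32) ≈ 0.907. The stated 90% is reproduced as power per comparison.

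**2. Planning responder shares.** With dispersion 1 the chance of no PE by time t (years) is S(t) = 1/(1 + μt). At one year this is 1/2.2 = 0.4545 on placebo and 1/1.84 = 0.5435 on brensocatib. The odds are 1/μ, so the odds ratio is 1.2/0.84 = 1.429.

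**3. Chance that a PE-free death at t is imputed a responder.** This is S(1)/S(t) = (1 + μt)/(1 + μ).

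| Death at | Placebo | Brensocatib |
|---|---|---|
| Month 3 | 1.30/2.2 = 0.59 | 1.21/1.84 = 0.66 |
| Month 6 | 1.60/2.2 = 0.73 | 1.42/1.84 = 0.77 |
| Month 9 | 1.90/2.2 = 0.86 | 1.63/1.84 = 0.89 |

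With deaths spread evenly over the year and weighted by the chance of still being PE-free, the average is S(1) ÷ [ln(1 + μ)/μ]: 0.4545/0.657 = 0.69 and 0.5435/0.726 = 0.75. The chance is below one half only for placebo deaths before about week 4.3.

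**4. Stress check with constant Phase 2 hazards.** h = −ln(1 − q)/(24/52) gives 1.43, 0.83 and 0.88 per year for placebo, 10 mg and 25 mg. The chance is exp[−h(1 − t)]. On placebo it is 0.34, 0.49 and 0.70 at months 3, 6 and 9. The placebo average is 0.45 (weighted) to 0.53 (even death times). The 10 mg and 25 mg averages are 0.64 to 0.68 and 0.62 to 0.67.

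**5. Effect on the odds ratio.** Phase 2 suggests a scale of (1/256) × (52/24) = 0.85% deaths per year.
- Deaths per arm: 540 × 0.0085 = 4.6. PE-free: 4.6 × 0.657 = 3.0 (placebo) and 4.6 × 0.726 = 3.3 (brensocatib).
- Imputed responders: about 2.1 and 2.5, or 0.39% and 0.46% of 540. The arms differ by 0.07 percentage points.
- With deaths as non-responders the shares are 0.9915 × 0.4545 = 0.4507 and 0.9915 × 0.5435 = 0.5389. The odds are 0.8204 and 1.1685, and the odds ratio is 1.424 instead of 1.429.
- If brensocatib deaths double, the share is 0.983 × 0.5435 = 0.5342, the odds 1.1470 and the odds ratio 1.398.
- Over assumed death rates of 0.25% to 2% the odds ratio is 1.427 to 1.419 (equal) or 1.420 to 1.358 (brensocatib doubled).

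**6. PEs imputed after death.** From Appendix I, E[Y2] = (1/c + Y1) μT2/(1/c + μT1). Take a death at week 26 (T1 = T2 = 0.5).
- Severe PEs, with the death as the only event (Y1 = 1): for an assumed rate of 0.05 and c = 1, 2 × 0.025/1.025 = 0.05. For a rate of 0.3 and c = 3, 1.333 × 0.15/0.483 = 0.41.
- Counting the death in Y1 multiplies the imputed number by (1/c + 1)/(1/c) = 1 + c, that is 2 to 4 times. At the SAP's example delta of 1.9 the range is 0.09 to 0.79.
- Primary endpoint, 8.2.2, Y1 = 0, c = 1, placebo: 0.6/1.6 = 0.375 PEs after death.

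**The case against.** The strongest reply is that post-withdrawal imputation is a declared choice. Protocol 10.4.6.1.3 states a missing-at-random assumption for the primary endpoint and acknowledges a hypothetical strategy for early study withdrawal. Making death a failure turns the endpoint into a composite, while time to first PE still censors these deaths and the PE rate merely shortens their time at risk. That is partly an estimand preference, and it stands as a cost of the fix. It does not supply a rule for death, since the declared reasoning concerns living people who leave.

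Three further points limit the concern.
- A reader might infer that imputing deaths contradicts the SAP's own responder definition. It does not: the imputation branch in 6.7.2 explicitly qualifies the completion condition, for every dropout.
- A reader might infer that deaths from other causes also count as success under the Composite estimand. The text does not settle this. SAP 6.7.2 makes the On-Study criteria a minimum there, which could fail such a death, and 8.3.2.2 describes no imputation, only a similar logistic model.
- A reader might infer that most imputations of these deaths are responders in any case. This depends on the model: on placebo it is 45% to 53% under Phase 2 hazards. The SAP imputes from a covariate-adjusted piecewise exponential model, whose longest imputable time could not be checked from the text available.

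The tipping-point analyses are conditional and carry no alpha, and 8.3.4.2 discloses its changed event definition. Post-death imputation there follows from the absence of a stopping rule, not from an explicit instruction.

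**Conclusion.** The gap is real and its likely effect is very small. As written, the On-Study responder analysis treats a PE-free death exactly like a living dropout, so a death can be classed as success under H5 or H6. Sections 8.2.2 and 8.3.4.2 likewise impute PEs for time after death, and 8.3.4.2 inflates the number through Y1.

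The probabilities rest on the planning rates with dispersion 1. The odds ratios also assume evenly spread deaths unrelated to PE risk, at a rate borrowed from a single Phase 2 death. A reader might infer that the responder result is materially biased. The documents do not support that: bias needs an imbalance in deaths between arms, and nothing in them points to one. The case for acting is that the rule should be fixed before unblinding and costs little.

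**What to change.** 1. In Appendix I, Table 19, set T2 = 0 for participants who die, for both 8.2.2 and 8.3.4.2. The table's notes already make Y2 zero when T2 is zero, so no PEs would be imputed after death.
2. In 6.7.2, 8.3.2.1 and Appendix I, class a participant who dies before Week 52 as a non-responder in every imputed data set, in keeping with the completion condition. Impute only survivors who left. State the same rule for the Composite estimand, which removes the ambiguity about non-NCFBE deaths.
3. Optionally, run 8.3.4.2 on the main severe-PE definition so that its delta = 1 cell corresponds to 8.3.4.1, and report the version that counts death as a severe PE separately.

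The cost is SAP wording and a few lines of code. The downside is that the responder odds ratio then includes all-cause death and handles deaths differently from the time-to-first-PE and rate endpoints; the SAP should say so.

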#### 8.3.2.2. Sensitivity / Supplementary Analyses

The supplementary Estimand for the responder status for exacerbation-free over the 52-week treatment period is the Composite Estimand (see Section 2) and will utilize the ITT Analysis Set (see Section 5.2). The derivation of the endpoint is detailed in Section 6.7.2. A similar logistic regression model as for the On-Study Estimand will be used for the responder status data of the Composite Estimand.

#### 8.3.3. Change from Baseline in Post-bronchodilator FEV1 (L) at Week 52

#### 8.3.3.1. Main Analyses

The Main Estimand of the change from baseline in post-bronchodilator FEV1 (L) at Week 52 is the On-Study Estimand in which all observed data will be included in the analysis (see Section 2). The ITT Analysis Set (see Section 5.2) will be used for this Estimand. The derivation of the endpoint is detailed in Section 6.7.3. Tabulations described below will not be limited to Week 52 but summarize all scheduled time points.

Pre- and post-bronchodilator FEV1 assessments at baseline and Weeks 16, 28, 40, 52 will be summarized by treatment group using descriptive statistics. The summary will include changes from baseline, too.

Change from baseline in post-bronchodilator FEV1 (L) will be analyzed using a linear repeated measures model including treatment group, visit, treatment-by-visit interaction, sputum sample being classified as positive or negative for *Pseudomonas aeruginosa* at Screening Visit, the number of prior PEs [<3 or  $\ge$ 3] in the previous 12 months, stratification region (North America, Europe, Japan, and the Rest of the World), and age group (adult, adolescent) as fixed effects, and baseline value as covariate. The variance-covariance structure will be compound symmetric with the robust sandwich variance estimator (option EMPIRICAL in the PROC-Statement). This analysis will be performed in SAS using MIXED procedure. The OM option will be used to adjust the coefficients for the LSMEANS to reflect the observed data.

If the age group covariate creates estimability issues, it may be removed. If the model still does not converge after removing the age group covariate, other handling including using the parametric covariance estimator instead of the robust sandwich covariance estimator may be applied. When using the parametric covariance estimator, the restricted maximum likelihood (REML) estimator will be applied, with the variance-covariance structure being applied with the following sequence: UN -> TOEPH -> ARH(1) -> CSH. If the model still does not converge, the maximum likelihood estimator will be applied instead of the REML estimator, with the same sequence of the possible variance-covariance structures. The adjustment will be added to the footnote of the corresponding outputs.

The adjusted means in each treatment group, the adjusted mean differences between treatments, and their 95% Cis at Week 52 will be presented. The p-value for the adjusted mean difference will be compared to the appropriate alpha level per the multiple test procedure.

A figure displaying the adjusted mean changes from baseline over time by treatment group will be provided.

CONFIDENTIAL Page 60 of 139

